1.2. Hypothesis

Based on the primary endpoint, the percent change in body weight at Week 24 from Baseline in the Immediate Switch Arm (D/C/F/TAF FDC) is less than that of the Delayed Switch Arm (INI + TAF/FTC ARV).

[figure not shown]
1.3. Trial Design

This is a randomized, 48 week, active-controlled, open-label, prospective, multicenter, Phase 4 study to evaluate the tolerability of switching to D/C/F/TAF FDC compared to continuing the current INI + TAF/FTC ARV regimen in virologically-suppressed HIV-1 infected adult participants who have experienced rapid and significant body weight gain while receiving an INI + TAF/FTC ARV regimen. Figure 1 described three phases conducted in this study: Screening (approximately 30 days [up to a

Approved, Date: 24 March 2023

maximum of 6 weeks]), Open-Label Treatment (48 weeks), and Follow-up (for any participant who has an ongoing adverse event (AE) or serious adverse event (SAE) at the time of his/her last study visit).

Figure 1: Schematic Overview of the Study

Approximately 110 subjects will participate in this study. A maximum enrollment of approximately 70% male participants will be utilized to ensure adequate recruitment of female participants. A maximum enrollment of approximately 70% non-black participants will be utilized to ensure adequate recruitment of diverse races.

After obtaining the informed consent form (ICF) from the participant, selection criteria will be reviewed to confirm the participant's eligibility. At baseline (Day 1), participants who meet all eligibility criteria will be randomized in a 1:1 ratio to one of the following two treatment arms in an open-label manner. Randomization will be stratified by sex (Male or Female) and race (Black/African American or Non- Black/African American) at Baseline.

Eligible participants are to:

- have documented HIV-1 infection currently treated with a stable ARV regimen consisting of an INI combined with TAF/FTC for ≥6 consecutive months preceding the screening visit,
- body mass index (BMI) of ≥18 kg/m² at the time of starting an INI + TAF/FTC ARV regimen,
- have a rapid and significant weight gain, defined as a ≥10% increase in body weight within a 12-to-36 month time period while on the current INI + TAF/FTC ARV regimen,
- be virologically suppressed, with at least 1 plasma HIV-1 RNA measurement <50 copies/mL occurring between 12 and 2 months prior to screening while being on the stable INI + TAF/FTC ARV regimen and having HIV-1 RNA<50 copies/mL at the screening visit,
- Not have had previous failure on DRV treatment or known documented history of ≥ 1 DRV resistance associated mutations (RAMs).

The study will consist of three phases:

- Screening (approximately 30 days [up to a maximum of 6 weeks])
- Open-Label Treatment (48 weeks)
- Follow-up (for any participant who has an ongoing AE or SAE at the time of his/her last study visit).

Screening Phase

The informed consent form (ICF) must be signed before any study-specific procedures at the start of the Screening Phase. After obtaining the ICF from the participant, selection criteria will be reviewed to confirm the participant's eligibility. At baseline (Day 1), participants who meet all eligibility criteria will be randomized in a 1:1 ratio to one of the following two treatment arms. Randomization will be stratified by sex (Male or Female) and race (Black/African American or Non-Black/African American) at Baseline. All enrolled participants will be assigned randomized treatments in an open-label manner.

- **D/C/F/TAF FDC Arm (Immediate Switch):** Switch to a regimen of DRV 800 mg + COBI 150 mg + FTC 200 mg + TAF 10 mg FDC once daily, (n=55) for 48 weeks;
- Active-Control Arm (Delayed Switch): Continue current INI + TAF/FTC ARV regimen, (n=55) for 24 weeks. After 24 weeks participants will switch to a regimen of DRV 800 mg + COBI 150 mg + FTC 200 mg + TAF 10 mg FDC once daily for an additional 24 weeks.

Treatment Phase

Participants randomized to the Immediate Switch Arm must start D/C/F/TAF FDC within 24 hours of the Baseline visit and will continue to receive D/C/F/TAF treatment for a total of 48 weeks.

Participants randomized to the Delayed Switch Arm will continue their current INI + TAF/FTC ARV regimen for 24 weeks. After Week 24, all participants in the Delayed Switch Arm will be given the option to receive the D/C/F/TAF tablet and will be followed for an additional 24 weeks.

- D/C/F/TAF FDC Arm (Immediate Switch): Switch to a regimen of DRV 800 mg + COBI 150 mg + FTC 200 mg + TAF 10 mg FDC once daily, (n=55) for 48 weeks;
- Active-Control Arm (Delayed Switch): Continue current INI + TAF/FTC ARV regimen, (n=55) for 24 weeks. After 24 weeks participants will switch to a regimen of DRV 800 mg + COBI 150 mg + FTC 200 mg + TAF 10 mg FDC once daily for an additional 24 weeks.

Participants will return for study visits at Weeks 4, 12, 24, 36, and 48. Additionally, participants randomized to the Delayed Switch Arm will have an additional study visit at Week 28 (i.e., 4 weeks after switching from the INI + TAF/FTC ARV regimen to D/C/F/TAF FDC).

Key metabolic assessments include body weight measurements, body composition assessed via dualenergy X-ray absorptiometry (DEXA) scan, waist circumference measurements, vital sign measurements, select clinical laboratory tests (including fasting lipids, fasting glucose, homeostatic

model assessment of insulin resistance [HOMA-IR], HbA1c, leptin, adiponectin), and liver biomarkers.

Key efficacy assessments include HIV-1 viral load, CD4+/CD8+ cell count, and HIV-1 genotype/phenotype resistance testing, if necessary.

Key safety assessments include AEs, physical examinations, standard clinical laboratory tests, and pregnancy testing. Concomitant medications will be recorded. D/C/F/TAF FDC study intervention accountability and reasons for non-adherence will be monitored.

Patient Reported outcomes (PROs), including body shape questionnaire [BSQ-8D], DAILY EATS, HIV-Symptom Index [HIV-SI], and patient global impression of change [PGIC]), will be completed.

Unscheduled visits can be conducted as needed based on individual tolerability issues, or virologic reasons (i.e., suspected virologic rebound) that occur between scheduled visits.

HIV-1 genotypic and phenotypic resistance testing (PhenoSense GT® Plus Integrase¹) will be performed for participants with confirmed virologic rebound (2 consecutive HIV-1 RNA values \geq 200 copies/mL at a scheduled or unscheduled visit) and an HIV-1 RNA \geq 400 copies/mL at the time of confirmed rebound. The confirmatory testing should be conducted 2 to 4 weeks after the initial HIV-1 RNA value \geq 200 copies/mL. If genotypic/phenotypic resistance to study intervention is determined, study intervention may be discontinued, and the participant will be referred for continued medical care outside of the study if the decision is made to discontinue study intervention.

Plasma concentrations of DRV and COBI may be determined in participants experiencing virologic rebound using stored blood samples collected throughout the study, if deemed necessary. Plasma concentrations of INIs for the Delayed Switch Arm may be determined in participants experiencing virologic rebound using stored blood samples collected throughout the study, if deemed necessary.

The end of the study is defined as completion of the last data collection visit for the last participant participating in the study. For the purpose of the primary analysis, a participant will be considered to have completed the study if data collection as required per protocol through the complete course of 24 weeks of ART has been completed. The primary analysis of this study will be performed once all participants have completed the Week 24 visit or discontinued earlier. Additionally, data collected beyond Week 24 visit, including metabolic data, adverse events and other pertinent data, will also be summarized in the primary analysis. An interim analysis (IA) will be performed when approximately 60% of the planned 110 participants have completed the Week 12 visit and approximately 30% of participants have completed the Week 24 visit to assess sample size re-estimation (SSR) unblinded to ensure adequate power for the hypothesis testing for the primary endpoint.

Early Study Intervention Discontinuation (ESID): Participants who prematurely discontinue study intervention but have not withdrawn consent will be required to complete ESID assessments as soon as possible but within no later than 1 week of discontinuing study intervention.

At the end of the study (or at ESID), participants will resume routine clinical care with the care provider who will determine their future care. In anticipation of transitioning the participant to routine clinical care at the end of the study (or early discontinuation), the investigator should take steps to

ensure that the participants' ART is not interrupted.

Follow-up Phase

A follow-up visit is required for any participant who has an ongoing AE or SAE after completion of the last study-related visit (unless consent is withdrawn). These participants are required to return to the site 30 days (± 7 days) after completion of the last study-related visit (unless consent is withdrawn) and complete all procedures indicated in the Schedule of Activities (SoA).

1.4. Statistical Hypotheses for Trial Objectives

The primary goal of this study is to assess the percent change in body weight at Week 24 from Baseline of D/C/F/TAF FDC (Immediate Switch arm) in HIV-1 infected participant who are virologically-suppressed (HIV-1 RNA <50 copies/mL) and have experienced rapid and significant body weight gain in combination with an INI + TAF/FTC ARV regimen (Delayed Switch arm). The statistical hypothesis is the following:

 H_0 : Dt-Dc=0 versus H_1 : Dt-Dc \neq 0.

Where H_0 is the null hypothesis, H_1 is the alternative hypothesis; Dt= percent change in body weight at Week 24 from baseline for treatment D/C/F/TAF (Immediate Switch arm), Dc for the Delayed Switch arm.

The statistical hypothesis will be tested using repeated measures longitudinal method (linear mixed- effects (LME) model) at 0.05 significance level, 2-sided.

For all participants who receive at least 1 dose of study intervention, the descriptive statistics will be provided. Participant information will be analyzed based on the Intent-to-treat (ITT) population, unless otherwise specified.

Primary Endpoint Analyses: Percent change in body weight at Week 24 from Baseline. The primary endpoint analyses will be based on the ITT population. It will be evaluated using LME model with participant as random effect adjusted by baseline BMI and stratification factors (sex and race) in a longitudinal data with repeated measures (percent change in body weight measured at multiple visits).

1.5. Sample Size Justification

[figure not shown]
Using a T-test with 80% power to detect a difference of 3% at the significance level of 0.05, 2-sided, the sample size per treatment arm is a simple function of effect size (ES): $n_{arm}=16/(ES)^2$. The effect size is the standardized difference: $ES=\Delta/\sigma$, where Δ is the difference between the two arms, and σ^2 is the common variance. Since there was no direct data on the study population to assume the observed difference, Δ =3% is considered a clinical meaningful difference. Internal data from 2 Phase 3 studies^{2, 3} on D/C/F/TAF FDC arm from different HIV patient populations (naive, switch) have shown the %body weight change in the range of 1.5% to 1.8% and standard deviation from 4.0 to 4.6 (Table 1 and Figure 2), resulting a range of ES and corresponding sample size³.

Table 2 Phase 3 Studies on D/C/F/TAF FDC Arm

Study	AMBER D/C/F/TAF arm	EMERALD D/C/F/TAF arm
N % body weight change from baseline at week 24 (SD)	347 1.5 (4.6)	738 1.8 (4.0)
N % body weight change from baseline at week 48 (SD)	340 2.3 (5.0)	728 1.9 (5.1)

(Data on file)

Figure 2: Sample Size Estimation by Treatment Effect Size

Given the uncertainty of either the Δ or the variability, an adaptive unblinded SSR is planned to reestimate the sample size in an IA to ensure adequate power in the hypothesis testing for the primary endpoint using the conditional power approach. An initial sample size of 55 participants per treatment arm (110 participants total) will be used for treatment effect size of 0.54 (ADDPLAN version 6). The IA is planned when approximately 60% of the initial planned 110 participants have completed the Week 12 visit and approximately 30% of participants have completed the Week 24 visit to re-estimate the sample size to ensure adequate power for the hypothesis testing. All cumulative data will be used for the IA. The planned maximum total sample size after SSR is 150 participants. Details for the SSR,

threshold for the conditional power, and protection of overall significance level will be provided in the statistical plan for the IA and monitoring.

1.6. Randomization and Blinding

1.6.1. Procedures for Randomization

Participants will be randomly assigned to one of two intervention arms based on a computer-generated randomization schedule prepared before the study by or under the supervision of the sponsor. Randomization will be based on a computer-generated schedule, constructed via random permuted blocks to ensure balance across treatment arms in each strata of the stratification factors (sex and race), and prepared before the start of the study by the sponsor.

Central randomization will be implemented in this study. Participants will be randomized in a 1:1 ratio to the Immediate Switch Arm (D/C/F/TAF FDC starting on Day 1 for 48 weeks), or the Delayed Switch Arm (continue current INI + TAF/FTC ARV regimen for 24 weeks then switch to D/C/F/TAF for an additional 24 weeks).

Randomization will be stratified by sex (Male or Female) and race (Black/African American or Non-Black/African American) at Baseline. A maximum enrollment of approximately 70% male participants will be utilized to ensure adequate recruitment of female participants. A maximum enrollment of approximately 70% non-black participants will be utilized to ensure adequate recruitment of diverse races.

The randomization and baseline visit (Day 1) cannot proceed until the investigator has received all results of the screening visit and participant eligibility has been confirmed in interactive web response system (IWRS), which should occur within approximately 30 days after the screening visit (for further details, see Section 8 in Protocol). It is the responsibility of the investigator to ensure that the participant is eligible for the study prior to enrollment. Randomization should be performed on the same day as the baseline visit (Day 1), provided that all screening procedures have been completed and participant eligibility has been confirmed.

The IWRS will assign open-label kit numbers at each study visit. Study drug will be dispensed to the participant in an open-label fashion. The requestor must use his or her own user identification and personal identification number when contacting the IWRS, and then will give the relevant participant details to uniquely identify the participant.

1.6.2. Blinding

As this is an open-label study, blinding procedures are not applicable.

2. GENERAL ANALYSIS DEFINITIONS

2.1. Treatment Arms

Following notations for the treatment arms will be used:

- **D/C/F/TAF FDC Arm (Immediate Switch):** Switch to a regimen of DRV 800 mg + COBI 150 mg + FTC 200 mg + TAF 10 mg FDC once daily, (n=55) for 48 weeks.
- Active-Control Arm (Delayed Switch): Continue current INI + TAF/FTC ARV regimen, (n=55) for 24 weeks. After 24 weeks participants will switch to a regimen of DRV 800 mg + COBI 150 mg + FTC 200 mg + TAF 10 mg FDC once daily for an additional 24 weeks.

2.2. Visit Windows

As subjects do not always adhere to the protocol visit schedule, the following rules are applied to assign actual visits to analysis visits. Listed below are the visit windows and the target days for each visit. The reference day is Study Day 1. If a subject has 2 or more actual visits in one visit window, the visit closest to the target day will be used as the protocol visit for that visit window. The other additional visit(s) will not be used in the summaries or analyses, but they can be used for determination of clinically important endpoints. If 2 actual visits are equidistant from the target day within a visit window, the later visit is used.

All assignments will be made in chronological order. Once a visit date is assigned to a visit window, it will no longer be used for a later time point except for the endpoint. Listed below (Table 2) are the analysis time points (week), visit windows and the target days for each visit defined in the protocol during the treatment phase. The time intervals will be used for reporting of metabolic/weight, efficacy, and safety data.

Table 2. Visit Windows

	Immediate Switch Arm - Time	Delayed Switch Arm - Time	
Analysis	Interval	Interval	Target Time
Time Point a	(Day)	(Day)	Point (Day)
Screening	Day-42 - <day 0<="" td="">Day-42 - <day 0<="" td="">-∞	</day>	</day>	Day-42 - <day 0<="" td="">-∞	</day>	-∞
Baseline b	≤Day 1	≤Day 1	1
Week 4	Day 2 – Day 56	Day 2 – Day 56	29
Week 12	Day 57 – Day 126	Day 57 – Day 126	85
Week 24	Day 127 – Day 210	Day 127 – Day 182	169
Week 28	NA	Day 183 – Day 224	197
Week 36	Day 211 – Day 294	Day 225 – Day 294	253
Week 48	Day 295 – Day 378	Day 295 – Day 378	337

^a For subjects discontinuing treatment early, data collected at that visit will count towards the time interval based on days relative to baseline.

Note: Target Time Point (Day)=Week $x\times7 +1$; Time Interval (Day), for example, Start day=127=(85+169)/2 and then obtain the previous interval End day=127-1=126. Similarly, for other intervals' Start day and End day.

Phases will be constructed for each subject as follows for adverse events, concomitant therapies, and for the determination of the worst-case/toxicity/change in the cross-tabulations.

^b The baseline visit (Day 1) cannot proceed until the investigator has received all results of the screening visit and participant eligibility has been confirmed.

Trial phase	Start date	End date
Screening	Minimum of date of signing the informed consent and date of the screening visit, no early than Day -42	1 day before start of treatment or day 1 of treatment whichever the last before first dose.
Treatment	Date of the first intake (after	For ongoing/completed subjects, in order of priority:
Phase I	randomization)	 For delayed switched arm, use first D/C/F/TAF intake date – 1;
		- For immediate switch arm, use Week 24 visit date; if missing then
		 Projected Week 24 visit date
		Projected Week 24 visit date = first dose date $+ (7 \times 24)$.
		In case of withdrawal before Week 24 visit : Date of last intake +7 days. If the last dose date is missing, use the following date in order of priority:
		- The date of treatment termination + 7 days;
		- The first available follow-up visit date-1 day;
		- The earlier of projected Week 24 visit date +7 and Trial discontinuation date + 7, where projected Week 24 visit date = first dose date + (7×24).
Treatment	Treatment Phase I end date +1	For ongoing/completed subjects, in order of priority:
Phase II	day	- Week 48 visit date + 7; if missing then
		 Projected Week 48 visit date +7, where projected Week 48 visit date = first dose date + (7×48).
		In case of withdrawal after Week 24 visit: Date of last intake +7 days. If the last intake date is missing, use the following date in order of priority:
		- The date of withdrawal + 7 days;
		- The first available follow-up visit date-1 day;
		- The earlier of projected Week 48 visit date +7 and trial discontinuation date + 7, where projected Week 48 visit date = first dose date + (7×48).
*Follow-up	End of the last treatment phase +1 day	Trial termination date for all groups (date of last contact)

⁺¹ day contact)

*30 day follow-up visit required for any subject who has ongoing AE or SAE at the time of his last study visit.

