- d For participants randomized to the Delayed Switch arm; 4 weeks after switch to D/C/F/TAF FDC.
- e Participants who prematurely discontinue or change study intervention during the treatment phase (from Day 1 to Week 48) will be required to complete the early study intervention discontinuation (ESID) visit assessments within 1 week of stopping/changing study intervention.
- f Required for any participant who has an ongoing adverse event (AE) or serious adverse event (SAE) at the time of his/her last study visit (unless consent is withdrawn); ±7 days window may be used.

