- Study intervention should be continued if, in the assessment of the investigator, it does not result in risk to the participant. Remote medical consultation and clinical safety laboratory assessments (including home health visits) will allow continued study participation for participants in this trial. If at any time a participant's safety is considered to be at risk due to study intervention, study intervention will be temporarily or permanently discontinued, while every effort should be made to maintain follow-up on study.
- The benefit of continuing study intervention should be considered by the investigator for each individual participant, considering the potential impact of reduced direct clinical supervision on participant safety. A temporary interruption of study intervention might be considered based on investigator's discretion and documented.
- If study procedures cannot be performed per study protocol and are delayed, participants should stay on the assigned study intervention until these procedures can be performed.
- If a participant develops SARS-CoV-2 infection or related disease, the investigator should contact the sponsor to discuss plans for study intervention and follow-up. An interruption of study intervention should be considered by the investigator, depending on symptoms and concomitant medication used for the treatment of COVID-19. Treatment must be interrupted if prohibited medication is used. Standard Adverse Event/Serious Adverse Event reporting requirements apply.
- When a participant, for whom study intervention has been interrupted, recovers from suspected or confirmed SARS-CoV-2 infection or related disease and all toxicities improve to Grade ≤1, the investigator should discuss with the sponsor about resuming study intervention. If the study intervention has been interrupted for more than 4 weeks, the participant should be withdrawn from the study.
- Dispensing of D/C/F/TAF:
 - For participants unable to visit the study site, handover to a caregiver or delegate of D/C/F/TAF or direct-to-participant (DTP) shipment may be implemented, where allowed per local regulations and if requested by the principal investigator. Where handover to delegates or DTP shipments are deemed necessary, the process must be coordinated between the site staff and sponsor following standard DTP procedures for arranging shipment and adhering to associated approvals and documentation requirements.

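### SAP Table 2 closes the Delayed arm's Week 24 window at Day 182 whether or not the participant has switched, so a late pre-switch weight is lost to the primary endpoint and filed as Week 28

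*SAP*

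**What the plan says.** SAP 2.2 assigns visits to analysis time points by study day. In Table 2 the Week 24 window is "Day 127 – Day 182" in the Delayed arm and "Day 127 – Day 210" in the Immediate arm. Only the Delayed arm has a Week 28 window, "Day 183 – Day 224", with target Day 197. Boundaries are midpoints between target days; the table note gives the example "Start day=127=(85+169)/2 and then obtain the previous interval End day=127-1=126". Where several visits fall in one window, "the visit closest to the target day will be used as the protocol visit for that visit window", and a tie goes to the later visit. The windows apply to metabolic and weight data as well as efficacy and safety. The primary model (SAP 5.2.3) uses percent weight change at Weeks 4, 12 and 24 only.

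Footnote d of the Schedule of Activities (Protocol 1.3) describes the Week 28 visit: "For participants randomized to the Delayed Switch arm; 4 weeks after switch to D/C/F/TAF FDC". The Protocol's COVID-19 Appendix allows visits to be held remotely or delayed and adds that, when procedures are delayed, "participants should stay on the assigned study intervention until these procedures can be performed".

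The SAP does have a switch-based cut. For the end of Treatment Phase I it says "For delayed switched arm, use first D/C/F/TAF intake date", less one day. That rule serves adverse events, concomitant therapies and worst-case tabulations, not the assignment of weights to visits.

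**The concern.** Table 2 separates the Delayed arm's INI period from its D/C/F/TAF period at a fixed day, not at the actual switch. If a Delayed-arm Week 24 visit slips to Days 183 to 210 and the participant is still on the INI regimen, three things follow.

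- The weight is a genuine comparator-period weight, yet it does not count as Week 24. A weight on the same study day in the Immediate arm does.
- With no other weight in Days 127 to 182, the participant has no Week 24 value in the primary comparison. The reference value for the descriptive Week 24 to Week 48 consistency endpoints (SAP 6.2.1.1) is lost too.
- The weight is assigned to Week 28 and can be summarised there as an on-D/C/F/TAF value.

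This sits badly with SAP 5.2.2 and 5.2.3, which intend to use all available weight data. Other endpoints assigned by Table 2 are exposed as well. The COVID-19 Appendix foresees late DEXA scans, and a late pre-switch scan would be filed at Week 28, where no scan is scheduled.

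**Working it through.** **Inputs.** Target day = 7 × week + 1 (Table 2 note): Week 24 = 169, Week 28 = 197, Week 36 = 253. Visit tolerance is ±7 days (Protocol 1.3, footnote c). Planned size is 55 per arm for an effect size of 0.54 (SAP 1.5).

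**1. Reproducing the plan's boundaries.**
- Delayed arm: (169 + 197)/2 = 183, so Week 24 ends on Day 182, as stated.
- Immediate arm, with no Week 28 target: (169 + 253)/2 = 211, so Week 24 ends on Day 210, as stated.

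**2. Lateness each arm tolerates.** The protocol's Week 24 visit is Day 162 to 176.

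| | Delayed | Immediate |
|---|---|---|
| Days past target 169 | 182 − 169 = 13 | 210 − 169 = 41 |
| Days past Day 176 | 182 − 176 = 6 | 210 − 176 = 34 |

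The arms differ on Days 183 to 210, which is 28 days.

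**3. Which weight becomes Week 28.** Suppose the late visit and the switch fall on day d and the true Week 28 visit on d + 28.
- For d up to 196, both visits lie in Days 183 to 224. The pre-switch weight is chosen when 197 − d < (d + 28) − 197, that is, when d > 183.
- d = 183: distances 14 and 14, a tie, so the later (true) visit is used.
- d = 184: 13 against 15, so the pre-switch weight is used.
- d = 190: 7 against 21, so the pre-switch weight is used.
- d = 196: 1 against 27, so the pre-switch weight is used.
- d = 197 to 210: the true visit is on Day 225 to 238, inside the Week 36 window, so the pre-switch weight is the only Week 28 record.

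On this schedule the pre-switch weight is the analysed Week 28 value on Days 184 to 210, that is, 27 of the 28 days.

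**4. Size of the loss.** Each affected participant is 1/55 = 1.8% of the Delayed arm. The documents give no late-visit rate, so the rates below are assumptions. Two-sided t-test at 0.05, effect size 0.54, 55 in the Immediate arm:

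| Assumed Delayed-arm loss | Delayed n | Power |
|---|---|---|
| 0% | 55 | 80.1% |
| 5% | 52 | 79.0% |
| 10% | 50 | 78.2% |
| 20% | 44 | 75.3% |

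These figures ignore what the repeated-measures model recovers from Weeks 4 and 12.

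**The case against.** The Day 182 cut has a purpose. It follows from the SAP's own midpoint rule, and for participants who switch on time it keeps on-D/C/F/TAF weights out of Week 24 from Day 183. That stands, and any change must preserve it.

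The trigger is narrow. A visit must be at least 14 days past target, 7 beyond the tolerance. The COVID-19 Appendix prefers an on-site Week 24 visit within ±7 days, then tele-health, and supplies portable scales for home weighing. This limits the number affected; it does not rule the case out, because the same appendix permits delay.

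Not every Delayed-arm weight on Days 183 to 210 is a comparator weight. A tele-health Week 24 contact combined with direct shipment of D/C/F/TAF could put the first in-person weight after the switch, and Table 2 would then rightly exclude it from Week 24. The point is confined to weights taken before first intake.

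The relabelling in step 3 assumes Week 28 falls 28 days after the switch, as footnote d indicates. Footnote c schedules visits from baseline. If Week 28 is held near Day 197, the true visit can be selected; the late weight is then left out of the summaries but is still lost to Week 24.

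SAP 5.2.3 and 5.2.4 assume missing at random, add control-based imputation and include a sensitivity analysis without participants affected by COVID-19. These soften the consequence, but none of them restores a weight that was actually measured.

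A reader might infer that the rule biases the primary contrast, or pulls a 4-week switch effect toward zero. The documents support neither. Nothing shows that late attenders differ in weight change in a known direction, and no listed endpoint is a Week 24 to Week 28 change.

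**Conclusion.** The point holds as a limited defect that should be corrected. Table 2 applies different timing rules to the two arms for the primary endpoint. It can discard an observed comparator weight and present it as Week 28. The conclusion rests on three conditions: a Delayed-arm Week 24 visit on Days 183 to 210, the participant not yet switched, and no other weight in Days 127 to 182. Few participants are likely to meet them; at an assumed 5% to 10% loss, the cost is about 1 to 2 percentage points of simple t-test power. The harm is avoidable asymmetry, lost data and mislabelled Week 28 summaries, not a demonstrated directional bias.

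It might also be inferred that Weeks 36 and 48 need new targets counted from the switch. That is not supported. Footnote c schedules visits from baseline, and a displaced Week 28 visit on Day 225 to 238 is 28 to 15 days from Day 253, so a Week 36 visit held within ±7 days would still be selected.

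**What to change.** In SAP 2.2, for weight and the other endpoints assigned by Table 2:

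- Let the Delayed arm's Week 24 window run from Day 127 to the earlier of Day 210 and the day of first D/C/F/TAF intake, using pre-dose values.
- For participants who switch, do not assign a value taken before first intake to Week 28.
- Add a line for Delayed-arm participants with no first intake, since Week 24 to Day 210 would otherwise overlap Week 28 from Day 183. SAP 1.3 still describes the switch as optional.
- Leave the Week 36 and 48 windows and targets unchanged, and also the separate Week 18-30 snapshot window (SAP 6.1.2), which is already common to both arms.

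The cost is SAP wording and minor programming; the first-intake date is already needed for the trial phases, and no new data are required. There are two small downsides. Some Delayed-arm Week 24 weights will be up to 41 days past target, as the Immediate arm already allows. When the switch visit falls on Days 197 to 210 and the next visit is 28 days later, Week 28 will be empty, which is preferable to a pre-switch value under that label.
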